6.0 Enrollment/Randomization

Following baseline assessments, patient-caregiver dyads ($N = 50$) will be randomly assigned to the ACT intervention or education/support condition in a 1:1 ratio using a stratified block randomization scheme to balance the groups by patient performance status (Eastern Cooperative Oncology Group scores 0 or 1 vs. 2).^{48, 50} We will stratify randomization by performance status because the decision to provide chemotherapy and other cancer treatments is often based on performance status.⁵¹ Randomization will be performed using a SAS procedure routinely employed by the IU Biostatistics Department. The study statistician will create the randomization procedure, and the PI will inform study therapists of their assigned patients. Other members of the study team will remain blind to participants' group assignment. All patients will be registered with the Indiana University Cancer Center Clinical Trials Office. Applicable regulatory documents must be completed and on file prior to registration of any patients.

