Aim 2. Given that this is a pilot study, our data analytic approach for Aim #2 will be to derive effect size estimates rather than test for statistical significance. A linear mixed-model repeated measures approach (SAS Proc-Mixed) will be used to examine ACT's effects on primary and secondary outcomes. For outcome measures that only patients or caregivers complete (e.g., patient fatigue interference or caregiver burden), models will include main effects of time (as categorical) and study group and the time-by-study group interaction. Treatment effects will be evidenced by the interaction between time and study group (i.e., group mean differences after the intervention but no such differences at baseline). Models will include random intercepts to account for nonindependence of individuals' scores across time. For outcomes reported by patients and caregivers (e.g., psychological flexibility), multilevel modeling for dyadic data will be used.^{83, 84} Models will include the main effects of time, study group, and social role (patient vs. caregiver) as well as all two and three-way interactions between these variables. The time x study group x role interaction will estimate the degree to which treatment effects are different for patients and caregivers. Dyadic models will include random intercepts for patients and caregivers, as well as the covariance between the intercepts to account for nonindependence across time and across partners.

Aim 3. To conduct data analyses for Aim #3, we will use logistic and Poisson regression models to explore the effects of ACT on patient and caregiver physical and mental health service use (e.g., number of patient ER visits, patient and caregiver use of counseling and/or psychiatric medication). Logistic and Poisson regression analyses are appropriate for binary and count outcome data, respectively. Analyses will examine study condition as a predictor of health service use over the entire study period, controlling for baseline service use. Support service referrals will be a covariate in analyses of mental health service use.

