Statistical power. Although our analyses focus on effect sizes rather than statistical significance, we calculated power for comparing primary outcomes (patient fatigue interference and caregiver burden) between study groups. With a sample size of 34 patients and 34 caregivers at 2 weeks post-intervention (assuming 15% attrition), we will have 80% power ($\rho=.05$, two-tailed) to detect a large intervention effect ($d=.99$) on either primary outcome in a linear mixed model.⁸⁵ ACT had large effects on distress and QoL outcomes in late-stage ovarian cancer patients ($d=.89-1.69$) compared to CBT³³ and a medium effect ($d=-.59$) on fatigue interference compared to education/support in metastatic breast cancer patients with moderate-severe baseline fatigue interference.³⁴

Missing data. All data will be assessed for missingness and multiple imputation with 50 imputed samples will be used.⁸⁶ We will also compare participants and those who decline participation or withdraw on demographic and medical factors using t-tests and Chi-square analyses. Further, we will carefully track study participation and try to understand the reasons for dropout and missing data wherever possible. Identifying potential dropout and missing data mechanisms will allow us to incorporate those factors as auxiliary variables for multiple imputation as well as full information maximum likelihood estimation method assuming Missing at Random in our future Phase II trial.

Potential covariates. T-tests and chi-square analyses will be performed to identify any group differences in potential baseline covariates (e.g., demographic and medical variables), and if there are differences these variables will be used as covariates.

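### Randomisation is stratified by performance status, but no Aim 2 model contains that factor and the covariate rule will almost never add it; the cost is a small loss of precision for post-intervention group differences

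*Combined protocol and SAP*

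**What the plan says.** Section 6.0 (Enrollment/Randomization) assigns 50 dyads 1:1 "using a stratified block randomization scheme to balance the groups by patient performance status", with strata 0 or 1 versus 2. It gives the reason: "We will stratify randomization by performance status because the decision to provide chemotherapy and other cancer treatments is often based on performance status".

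Section 11.0, Aim 2, then lists the model terms:

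- For outcomes that only one member of the dyad reports, which include both primary outcomes, "models will include main effects of time (as categorical) and study group and the time-by-study group interaction".
- For outcomes that both report, "Models will include the main effects of time, study group, and social role (patient vs. caregiver) as well as all two and three-way interactions".
- On the random part of the single-role models, "Models will include random intercepts to account for nonindependence of individuals' scores across time".
- On the estimand, "Treatment effects will be evidenced by the interaction between time and study group". A parenthesis explains this as arms whose means differ after treatment but did not differ before it.

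Performance status is in neither list. The one other route into a model is the Potential covariates paragraph of section 11.0. It compares the arms on baseline variables by t-test and chi-square, and "if there are differences these variables will be used as covariates". It sets no threshold.

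**The concern.** A factor used to restrict the randomisation normally belongs in the analysis. Stratified blocks remove most between-stratum variation from the true sampling error of a comparison between arms. A model without the stratum leaves that variation in its error term, so the model-based standard error can exceed the real one and the precision bought by stratifying is not collected.

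The covariate rule makes the omission systematic. It admits a variable because it is unbalanced, and performance status is the one variable the design sets out to balance. The factor singled out in advance is therefore the one the rule is least likely to admit.

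At stake is the precision of the Aim 2 effect sizes, which section 2.0 says will inform a larger trial. The point estimates are not biased by the omission.

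**Working it through.** **1. The plan's own figure.** Section 11.0 (Statistical power) gives 80% power for d = 0.99 with 34 analysed per role, two-tailed 0.05. A plain two-sample t-test with 17 per arm has noncentrality 0.99 × √(17/2) = 2.89 on 32 degrees of freedom, and power 0.799. The figure reproduces as a comparison of two arms at one visit. The post-intervention group difference is therefore a contrast the plan uses, alongside the time-by-group interaction.

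**2. Can the covariate rule select the stratum?** Assume blocks of 4 and, for example, 14 of 50 patients scoring 2. Three full blocks split 6:6, and the last two patients at worst go to the same arm, giving 8 versus 6. The other 36 patients fill nine blocks and split 18:18. Then chi-square = 50 × (8×18 − 6×18)² / (26 × 24 × 14 × 36) = 0.21, p = 0.65. In simulation (4000 trials per setting, block sizes 2 to 8, 20% to 50% scoring 2) the test reached p < 0.05 in none under stratified blocks. Without stratification it did so in about 5% to 7%.

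**3. Post-intervention group difference.** Let performance status explain a share R² of outcome variance. The unadjusted model uses the total variance and the adjusted model uses the fraction 1 − R², so the ratio of standard errors is about 1/√(1 − R²). With 30% scoring 2, the gap δ between strata, in within-stratum SDs, follows from 0.3 × 0.7 × δ² = R²/(1 − R²). The last column is the interval-width ratio from a simulation of one follow-up outcome (50 dyads, blocks of 4, 6000 replicates per row).

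| R² | δ | 1/√(1 − R²) | Simulated ratio |
|---|---|---|---|
| 5% | 0.50 | 1.026 | 1.025 |
| 10% | 0.73 | 1.054 | 1.055 |
| 20% | 1.09 | 1.118 | 1.120 |
| 30% | 1.43 | 1.195 | 1.197 |

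Simulated coverage of the nominal 95% interval without the stratum was 95.3%, 96.2%, 97.1% and 97.9%. With the stratum it was 94.5% to 95.1%.

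**4. Time-by-group change contrast.** This contrast is within-person, so a stratum effect that is the same at every visit cancels. With unit within-stratum variance, assumed within-person correlation 0.5 and 25 per arm, the standard error is √(2 × (1 − 0.5) × 2/25) = 0.283 whether or not the stratum is in the model. Simulated random-intercept fits agree (three visits, 35% scoring 2, 1000 trials per row). The entries are mean standard errors for change to the first follow-up:

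| Scenario | Stratum omitted | Main effect added | Stratum × time added |
|---|---|---|---|
| Constant effect 0.5 SD, no dropout | 0.282 | 0.282 | 0.282 |
| Constant effect 1.0 SD, no dropout | 0.281 | 0.281 | 0.281 |
| Constant effect 0.5 SD, 15% dropout | 0.300 | 0.300 | 0.301 |
| Effect on change 0.5 SD, no baseline effect, 15% dropout | 0.307 | 0.307 | 0.301 |

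Only the last row shows a gain: 0.307/0.301 = 1.02, about 2%. It comes from the interaction with time, not from the main effect.

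**The case against.** The strongest reply is that Aim 2 names the time-by-group interaction as the evidence of a treatment effect, and that contrast is unaffected by a constant stratum effect. For that contrast and that condition this stands in full: standard errors match with and without the stratum, and they agree with the empirical spread. It does not dispose of the point. The parenthesis in Aim 2 describes mean differences after treatment, and the power statement is sized on a two-arm comparison at one visit.

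Two further replies also stand. Aim 2 promises effect sizes rather than tests, and section 11.0 names no standard error or interval to be reported, so the harm arises only where precision is attached to those effect sizes. And any error in width is conservative.

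A reader might infer more than the documents support:

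- **That Aim 2 intervals are generally too wide.** This fails for the change contrast when the stratum effect is constant over time.
- **That the loss reaches 12% to 20%.** This needs performance status to explain 20% to 30% of variance, which is strata 1.09 to 1.43 SDs apart. Nothing in the documents supports effects that strong, and section 4.0 restricts entry to scores up to 2 and fatigue interference of at least 2.5. The stated reason for stratifying concerns treatment decisions, not outcome prediction, and no section says patient performance status predicts caregiver burden.
- **That Aim 3 suffers in the same way.** It does not. In simulation, adding the factor left the Poisson standard error unchanged (0.247 and 0.247 at a rate ratio of 2) and raised the logistic one (0.584 to 0.601 at an odds ratio of 2, 0.578 to 0.635 at 5), because the adjusted odds ratio is a different quantity from the marginal one.

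**Conclusion.** The mismatch is real: no Aim 2 model contains the stratification factor, and the covariate rule will almost never supply it. Its size is modest. For post-intervention group differences the standard error is overstated by about 2.5% to 5% if performance status explains 5% to 10% of outcome variance. For the change contrast the loss is nil under a constant stratum effect and about 2% in the scenario where performance status alters change.

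These figures rest on assumptions the documents do not settle: block size, share scoring 2 (30% or 35% here), within-person correlation (0.5) and prognostic strength. The textual mismatch depends on none of them. For Aim 3, neither a claim about interval width nor a mandatory covariate follows.

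**What to change.** In section 11.0, Aim 2, state that every model includes the randomisation stratum (performance status 0 or 1 versus 2) and its interaction with time as fixed effects, regardless of observed balance. Specify the value used to randomise, because Table 2 shows patient-reported performance status collected again at both follow-ups. Under Missing data, add the stratum to the imputation model. Under Potential covariates, say that the balance screen does not govern this factor. The Aim 3 models can stay as they are on this point.

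The interaction with time matters: a main effect alone would leave the change contrast where it is. The cost is a sentence or two and about one degree of freedom per occasion, out of 34 − 2 = 32 for a two-arm comparison at the planned 34 analysed. No new data are needed, since the stratum is known for every randomised dyad.

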4.0 Eligibility Criteria

4.1 Patient Inclusion Criteria:

- Patient is at least 3 weeks post-diagnosis of unresectable stage III or stage IV gastrointestinal cancer (i.e., anal, colon, esophageal, gallbladder, liver, pancreatic, rectal, small intestine, or stomach cancer) and is receiving care at the Indiana University Simon Cancer Center or Eskenazi Health.
- Patient is at least 18 years of age.
- Patient has adequate English fluency for study participation.
- Patient is willing to participate in this study.
- Patient has moderate to severe fatigue interference (i.e., mean score ≥ 2.5 on the Fatigue Interference subscale of the Fatigue Symptom Inventory)^{36, 37}
- Patient has an eligible, consenting family caregiver (see criteria below)

4.2 Patient Exclusion Criteria:

- Patient makes 3 or more errors on a validated 6-item cognitive screener⁴⁷ or exhibits significant psychiatric or cognitive impairment (dementia/delirium, intellectual disability, active psychosis) that in the judgment of the investigators would preclude providing informed consent and study participation.
- Patient Generated Subjective Global Assessment (PG-SGA; the patient-reported version of the Eastern Cooperative Oncology Group score) >2 .⁴⁸
- Patient is receiving hospice care at screening.
- Patient does not have working phone service.
- Patient has hearing impairment that precludes participation.

Note: Patients who enroll in hospice during the trial will have the option of continuing trial participation.

4.3 Caregiver Inclusion Criteria:

- Family caregiver identified by an unresectable stage III or stage IV gastrointestinal cancer patient who meets the eligibility criteria.

- Caregiver lives with the patient or has visited the patient in-person at least twice a week for the past month.
- Caregiver is at least 18 years of age.
- Caregiver has adequate English fluency for study participation.
- Caregiver is willing to participate in this study.
- Caregiver has moderate to severe caregiving burden, defined as a score ≥ 6 on the 6-item Zarit Burden Interview³⁹ or a T-score ≥ 60 (at least one standard deviation above the population mean) on the 4-item PROMIS anxiety or depression measures.⁴⁹

4.4 Caregiver Exclusion Criteria:

- Caregiver exhibits significant psychiatric or cognitive impairment (dementia/delirium, retardation, active psychosis) that in the judgment of the investigators would preclude providing informed consent and study participation.

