Baseline and follow-up measures: Patients and caregivers will complete a baseline assessment and two follow-up assessments using the measures described below (see Appendices F-I). The baseline assessment takes about 30 minutes for patients and 25 minutes for caregivers. Each follow-up assessment takes about 25 minutes for patients and 20 minutes for caregivers. All self-report measures have strong evidence of reliability and validity. PROMIS measures were tested with over 21,000 people, including cancer patients.⁵⁵⁻⁵⁸ Validated non-PROMIS measures will be used for constructs that PROMIS measures do not currently assess (e.g., fatigue interference). Patients and caregivers in the ACT condition will also complete a 30-minute qualitative interview on intervention acceptability (see Appendix J). Baseline and follow-up assessments and qualitative interviews will be audio-recorded so that the PI or a trained member of the study team may audit them for adherence to the study protocol. [name], a qualitative methodologist, will randomly review at least 20% of qualitative interviews.

Demographic/medical factors. At baseline, patients and caregivers will report standard demographics (i.e., age, gender, race/ethnicity, marital status, education, income, employment status) and chronic medical conditions.^{59, 60} Caregivers will also report their relationship to the patient. Patients' cancer information will be collected via chart review (Appendix S).

Feasibility and acceptability data. Feasibility will be assessed by accrual rates, attrition, and adherence. At the 2-week follow-up, acceptability will be assessed with helpfulness ratings on a scale from 1 (did not help at all) to 5 (extremely helpful) for number and length of sessions, topics, therapist, and telephone format.⁵⁴ The RA will be blind to study condition, as the questions apply to either condition. For ACT participants, acceptability will also be assessed within 2 weeks of the 2-week follow-up via a 30-minute qualitative phone interview on the perceived helpfulness and impact of ACT components (see Appendix J for detailed interview guide). Qualitative interviews will be conducted with patients and caregivers separately. A doctoral student in clinical psychology with qualitative interviewing experience will conduct the interviews.

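### Aim 2 reads the treatment effect as a difference in change instead of adjusting for the baseline score, and it chooses covariates by baseline significance tests

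*Combined protocol and SAP*

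**What the plan says.** Under Aim 2, section 11.0 sets out a linear mixed model with categorical time, study group and their interaction, plus a random intercept. Baseline is one of the three visits in the outcome, and each arm has its own baseline mean. The plan then says "Treatment effects will be evidenced by the interaction between time and study group", which it explains as "group mean differences after the intervention but no such differences at baseline". The dyadic models add role and its interactions, again without the baseline score as a covariate. The aim is to "derive effect size estimates rather than test for statistical significance".

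Aim 3, in the same section, does adjust: it takes "study condition as a predictor of health service use over the entire study period, controlling for baseline service use".

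For other covariates, section 11.0 says "T-tests and chi-square analyses will be performed to identify any group differences in potential baseline covariates", and variables that differ are then put in the model. It gives no significance level, closed list of variables or form of entry. Section 6.0 stratifies randomisation by performance status (0 or 1 vs. 2), but the stratum is not named in the Aim 2 model.

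**The concern.** Section 6.0 begins "Following baseline assessments, patient-caregiver dyads" and then describes random assignment. Baseline scores therefore precede allocation, and the true difference between arms at baseline is zero. The planned model nevertheless estimates that difference freely and subtracts it in full. Subtracting the whole observed difference is right only if the slope of follow-up on baseline is 1. If the slope is smaller, the contrast over-corrects chance imbalance and carries extra variance.

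The second issue is that a significance test between randomised arms detects only chance. It says nothing about whether a variable predicts the outcome, so the fitted model depends on the draw.

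Aim 2 exists to produce effect sizes that will inform a larger trial application (section 2.0), so precision is what this analysis delivers. For fatigue interference, caregiver burden and the secondary outcomes, intervals may be wider than the same data allow.

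**Working it through.** **Inputs from the documents.** 50 dyads randomised 1:1 after baseline (section 6.0). 34 patients and 34 caregivers at 2 weeks, 15% attrition, 80% power, two-tailed .05, d = .99 (section 11.0). Since 34/.85 = 40 while 50 × .85 = 42.5, results are shown for 34 and for 42 dyads followed.

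**Assumptions.** The documents give neither the correlation ρ between baseline and follow-up nor the ratio r of baseline SD to follow-up SD. I use ρ = .3, .5, .7 and r = 1, plus r = .8 in case the entry cutoffs narrow the baseline spread. Section 4.1 requires "Patient has moderate to severe fatigue interference" on the same subscale that is the patient outcome. Follow-up SD is set to 1.

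**The plan's own figure.** Detectable d = (t.975,32 + t.80,32) × √(4/34) = (2.037 + .853) × .343 = .991. Exact power at d = .99 is 79.9%. The stated figure reproduces as a comparison of two groups of 17 with no gain from baseline. It matches the planned change contrast only if ρ = .5 (complete data, equal SDs).

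**What the planned interaction estimates.** In simulated complete data (34 subjects, three visits), the fitted interactions were -0.1703 and 0.0670, identical to the raw differences in change.

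**Complete data.** Var(change) ∝ r² + 1 − 2ρr and Var(adjusted) ∝ 1 − ρ². The gap is (r − ρ)², which is never negative. At r = 1 the ratio adjusted/change is (1 + ρ)/2 = .65, .75, .85. At r = .8 it is .78, .89, .98.

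**With dropout, r = 1.** With 25 baselines and n_c followed per arm, the planned variance is 2[(1 − ρ²)/n_c + (1 − ρ)²/25] and the adjusted variance is 2(1 − ρ²)/n_c. For n_c = 17:
- ρ = .3: .1071/.1463 = .732
- ρ = .5: .0882/.1082 = .815
- ρ = .7: .0600/.0672 = .893

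Estimating one baseline slope multiplies the adjusted variance by (n − 3)/(n − 4), where n is the number followed: 31/30 for 34 and 39/38 for 42. For r = .8 the planned model was evaluated with its best-fitting random-intercept covariance and its true (sandwich) variance. Variance ratios with the slope cost included:

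| Followed | r | ρ = .3 | ρ = .5 | ρ = .7 |
|---|---|---|---|---|
| 34 | 1 | .76 | .84 | .92 |
| 42 | 1 | .71 | .80 | .89 |
| 34 | .8 | .87 | .95 | 1.00 |
| 42 | .8 | .83 | .93 | 1.00 |

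**In effect-size terms (34 followed, slope cost included), planned to adjusted:**

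| | ρ = .3 | ρ = .5 | ρ = .7 |
|---|---|---|---|
| Detectable d, r = 1 | 1.10 to .96 | .95 to .87 | .75 to .72 |
| Detectable d, r = .8 | 1.03 to .96 | .90 to .87 | .72 to .72 |
| 95% CI half-width (SD), r = 1 | .78 to .68 | .67 to .62 | .53 to .51 |

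With 42 followed and r = 1, detectable d goes from 1.02 to .86, .87 to .78 and .68 to .64. In the dyadic models (34 of 50 followed, equal SDs, before the slope cost), the ratio for a role-specific effect is .72 to .73, .80 to .81 and .87 to .89 at the three values of ρ, for assumed intercept correlations between partners of 0 to .6.

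**Sensitivity to chance imbalance.** In 20,000 simulated trials per ρ, the slope of the change estimate on the observed baseline difference was -.68, -.51 and -.30; after adjustment it was about 0. One standard error of baseline imbalance in 50 dyads is √(4/50) = .28 SD. At ρ = .5 with complete data and equal SDs, that moves the planned estimate by (1 − .5) × .28 = .14 SD.

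**Covariate rule.** Section 7.0 lists seven variables: "standard demographics (i.e., age, gender, race/ethnicity, marital status, education, income, employment status". Adding one medical variable and assuming independent tests at .05, at least one is flagged by chance in 1 − .95⁸ = 34% of trials (30% for seven tests, 40% for ten). Conversely, a t-test on 50 dyads has only 41% power to flag a .5 SD imbalance. A flagged variable entered as a main effect cancels from the time-by-group contrast when data are complete. With R² = .2 and ρ = .5, the mean absolute shift was 0 with all 50 followed, .023 SD with 42 and .038 SD with 34.

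**The case against.** The planned model is a recognised longitudinal analysis and is unbiased under randomisation. The gain rests on two quantities the documents do not give. The 29% figure is the best case (ρ = .3, equal SDs, 42 followed); with 34 followed the maximum is 24%, and at ρ = .5 it is 16%, or 5% if r = .8. A narrowed baseline spread is plausible for fatigue interference because patients are selected on that subscale. It may be weaker for caregivers, who can also enter on anxiety or depression. At ρ = .3 or .5 the detectable effect stays far above the pilot's .59 under either analysis. The equality with a raw difference in change is exact only with complete data and no added covariates, and the planned multiple imputation was not modelled. Aim 3 has a single outcome over the whole period, so baseline naturally enters there as a covariate. The parenthesis about no baseline differences may simply describe an interaction pattern.

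All of this limits the size of the point, and the last two remarks mean that the comparisons with Aim 3 and with the parenthesis are only supporting arguments. None of it favours the planned contrast: in the settings examined, adjustment costs at most about 0.3% of variance.

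It can also be said that adding the stratum is pointless because omitting it costs essentially nothing. That is true of the planned change contrast, where a stratum main effect cancels. It does not cancel in a baseline-adjusted model. Charging it as a full second covariate gives detectable d of .98, .89 and .73 (34 followed, equal SDs), an upper bound because the stratum is balanced by design.

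**Conclusion.** The concern holds in both parts. Aim 2 has no baseline adjustment, and its covariates depend on baseline tests. The first costs precision and leaves the estimate sensitive to chance imbalance; it does not bias the randomised comparison. The variance reduction available is between 0% and about 29%, assuming ρ of .3 to .7 and a baseline/follow-up SD ratio of .8 to 1, without modelling imputation. The covariate rule has little numerical effect on the planned contrast; the case against it is that the model is not fixed in advance. Only the estimation-only Aim 2 is affected, not the feasibility or acceptability decision. The change should be made because it needs no new data and costs almost nothing.

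**What to change.** For each Aim 2 outcome, specify a repeated-measures model adjusted for the baseline score. Either enter baseline by visit as a covariate with the two follow-ups as outcomes, or keep all three visits and constrain the baseline means to be equal across arms. In the dyadic models, make the baseline terms role-specific. Report the treatment difference at each follow-up with a 95% CI.

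Replace the test-then-adjust rule with covariates named in advance, including the performance-status stratum as a single main effect. Present the baseline table descriptively, without tests.

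The cost is SAP wording; every variable is already collected. Counting one stratum term, single-role models have 7 fixed effects (baseline as covariate) or 6 (constrained means) against 6 planned. Dyadic models have 13 or 11 against 12.

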Target date = approximately 2 weeks after the last intervention session. Assessments can be completed as early as 7 days prior to this target follow-up date or as late as 14 days following the target follow-up date.	(5) Patients and caregivers will complete a 30-minute assessment over the phone (see "interview procedures" below). Assessments will be administered by a trained research assistant or a trained doctoral student in clinical psychology who are blinded to the intervention arm.
Target date = within 2 weeks of the 2-week post-intervention assessment. The qualitative interview can be completed as early as the same day as the 2-week follow-up or as late as 21 days after the 2-week follow-up.	(6) Patients and caregivers in the ACT condition will complete a 30-minute qualitative phone interview on intervention acceptability. The interview will be administered by a trained doctoral student in clinical psychology.
Target date = approximately 3 months after the last intervention session. Assessments can be completed as early as 7 days prior to this target follow-up date or as late as 21 days following the target follow-up date.	(7) Patients and caregivers will complete a 25- or 20-minute assessment over the phone, respectively. Assessments will be administered by a trained research assistant or a trained doctoral student in clinical psychology who are blinded to the intervention arm.

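### The single-role models name only random intercepts, which imposes one variance and one correlation over three unequally spaced visits, so the standard error of the 3-month effect may be misstated

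*Combined protocol and SAP*

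**What the plan says.** Section 11.0, Aim 2, sets out the model: "A linear mixed-model repeated measures approach (SAS Proc-Mixed) will be used to examine ACT's effects on primary and secondary outcomes". For outcomes that one role reports, "models will include main effects of time (as categorical) and study group and the time-by-study group interaction". The within-person dependence is handled in one sentence, which begins: "Models will include random intercepts to account for nonindependence". No random slope, residual covariance, robust standard error or degrees-of-freedom method is named. Baseline is one of the modelled visits, and "Treatment effects will be evidenced by the interaction between time and study group". The stated aim is to "derive effect size estimates rather than test for statistical significance", and no confidence interval is specified.

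Two design features bear on this.
- **Entry:** Section 4.1 requires a minimum score of 2.5 on the scale that is also the patient primary outcome: "Patient has moderate to severe fatigue interference (i.e., mean score". Section 7.0 places this test at screening. Table 1 (Section 5.0) places the baseline interview about a week after recruitment, and up to a month after.
- **Timing:** Table 1 puts the first follow-up about 2 weeks after the last session. For the second it says "Target date = approximately 3 months after the last intervention session".

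Section 11.0 also plans multiple imputation with 50 imputed samples.

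**The concern.** A random intercept with independent residuals implies compound symmetry: the same variance at every visit and the same correlation between every pair of visits. There is reason to doubt both here.

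On the target schedule, baseline to first follow-up is about 8 weeks (1 week to session 1, 5 weeks from session 1 to session 6, then 2 weeks). It is about 15 weeks if the sessions use all 12 weeks allowed (1 + 12 + 2). The two follow-ups are about 11 weeks apart (13 − 2). Baseline to 3 months is therefore the longest interval, at about 19 weeks or more, and its correlation may well be the lowest. Selecting patients on fatigue interference can also make the baseline variance smaller than the follow-up variances.

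The pilot is meant to supply effect sizes for a larger trial, and an effect size from about 50 dyads is useful only with an honest measure of its precision. A pooled covariance that does not fit gives the wrong precision for particular contrasts.

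**Working it through.** **The plan's own figure.** Section 11.0 states 80% power for d = 0.99 with 34 per role at 2 weeks, two-sided 5%. With 17 per arm and 32 degrees of freedom, the detectable d is (2.037 + 0.853) × √(2/17) = 0.991, and power at 0.99 is 0.799. The figure reproduces from a plain two-sample t-test. It uses no between-visit correlation, so it does not settle what follows.

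**Formulas (balanced, complete data).** Let D12, D13 and D23 be the variances of the differences between baseline (1), 2 weeks (2) and 3 months (3), and V1 to V3 the visit variances. Under random intercepts:
- change contrast: model SE / true SE at 3 months = √(mean of D12, D13, D23 ÷ D13);
- simple group difference: model SE / true SE at 3 months = √(mean of V1, V2, V3 ÷ V3);
- approximate coverage of a nominal 95% interval = 2Φ(1.96 × ratio) − 1.

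**Illustration (all inputs assumed).** Take a pre-selection SD of 2.2, a screening cutoff of 2.5, and correlations that decay with time. After selection the SDs are 1.83, 2.01 and 2.05, and the correlations are 0.51 (1–2), 0.42 (1–3) and 0.66 (2–3).
- Visit variances: 3.349, 4.040, 4.203; mean 3.864.
- D12 = 3.349 + 4.040 − 2(0.51)(1.83)(2.01) = 3.64
- D13 = 3.349 + 4.203 − 2(0.42)(1.83)(2.05) = 4.40
- D23 = 4.040 + 4.203 − 2(0.66)(2.01)(2.05) = 2.80
- Mean of the three = 3.61.
- 3-month change: √(3.61/4.40) = 0.906, coverage 92.4%. 2-week change: √(3.614/3.637) = 0.997.
- Simple group difference: √(3.864/4.203) = 0.959 at 3 months and √(3.864/4.040) = 0.978 at 2 weeks.

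**Which assumption drives the 3-month change result?**
- Same SDs, all correlations 0.53 (the mean of the three): D = 3.49, 3.57, 3.87; mean 3.65; ratio √(3.647/3.575) = 1.01, slightly too large.
- Equal SDs, same decaying correlations: D is proportional to 0.98, 1.16, 0.68; mean 0.94; ratio √(0.94/1.16) = 0.90.

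The narrowing comes from the assumed decay. The unequal variances contribute none of it.

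**Range for the 3-month change contrast.** The rows below assume literal truncation of baseline with 60% of patients above the cutoff. That is harsher than the design, because the cutoff acts on an earlier score. Coverage is simulated with 17 and 25 per arm.

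| Pre-selection correlations (1–2, 2–3, 1–3) | SE ratio | Coverage |
|---|---|---|
| 0.6, 0.6, 0.6 | 1.02 | 0.954–0.958 |
| 0.6, 0.6, 0.5 | 0.95–0.96 | 0.94 |
| 0.6, 0.6, 0.4 | 0.89–0.91 | 0.92 |
| 0.5, 0.4, 0.5 | 1.07 | 0.962–0.967 |

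With correlation falling by elapsed time, the ratio is 0.91 for gaps of 8 and 11 weeks (coverage 0.93) and 0.87 for gaps of 15 and 11 weeks (coverage 0.91). Decay with no selection at all (0.6, 0.6, 0.4) gives √(0.933/1.2) = 0.88 by formula and 0.89 with coverage 0.917 by simulation. A visit-specific variance of the unstructured type covered 0.94 to 0.96 in every scenario.

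**Simple 3-month group difference, patient fatigue.** Under literal truncation with equal correlations of 0.6, the variances are 0.42, 0.79 and 0.79, with mean 0.67. The ratio is √(0.669/0.792) = 0.92 (simulated coverage 0.935). With a screening-to-baseline correlation of 0.8, closer to the design, it is 0.95 to 0.96 (coverage 0.942). Adding decay (0.6, 0.6, 0.4) to literal truncation gives 0.88 to 0.89, but that mixes both mechanisms and overstates the selection described.

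None of these calculations models dropout or the imputation step.

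**The case against.** The strongest reply is that this is a pilot about effect sizes, that a random intercept is a common parsimonious choice at this sample size, and that the text does not exclude a separate residual structure. With complete data and a separate mean for each visit and group, the point estimates do not depend on the covariance. In the illustration the 2-week contrast, at the visit used for the power statement, is almost exactly right (0.997). All of this stands, and it limits the point to precision, mainly at 3 months.

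A reader might infer more than the documents support:
- **That the entry cutoff makes the 3-month interaction interval too narrow.** It does not. Selection alone leaves that ratio at 1.01 to 1.02. It narrows only the simple group difference. The plan's gloss on the interaction, which speaks of group differences after the intervention, leaves open which of the two will be reported.
- **That the primary outcome is truncated at baseline.** The cutoff applies to the screening score, and fatigue is measured again at baseline. Caregivers enter on the 6-item Zarit or a PROMIS anxiety or depression score, while their outcome is the 12-item Zarit. Sleep interference has no cutoff.
- **That incomplete cases will be wrongly weighted.** If missing outcomes are imputed as planned, each analysed data set is complete, and this argument loses most of its force. Imputation does not repair the standard error, because each completed data set is still fitted with the same covariance.

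**Conclusion.** The point holds as a gap in specification with a modest, assumption-dependent effect. As written, the single-role models impose equal variances and equal correlations, and no safeguard is named. Any standard error or interval for the time-by-group effect may be misstated:
- **Baseline-to-3-month contrast:** about 5 to 13% too small if correlation decays with time (coverage about 91 to 94%); about right or 1 to 2% too large with equal correlations; up to about 7% too large under other patterns.
- **Simple 3-month difference in patient fatigue:** selection can make it about 4% too small in the illustration and about 8% too small under literal truncation with equal correlations. This does not carry over directly to caregiver burden or sleep interference.

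A firm statement that the 3-month interval is too narrow would need between-visit correlations, which the documents do not give. Decay is plausible from the visit spacing, but it remains an assumption.

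**What to change.** For the single-role models (fatigue interference, caregiver burden, sleep interference), replace the random intercept with an unstructured within-person covariance over the three visits (in PROC MIXED, a REPEATED statement on visit with TYPE=UN and SUBJECT=id). State Kenward-Roger degrees of freedom. Name the fallbacks in advance if the model does not converge: heterogeneous Toeplitz, then heterogeneous compound symmetry. This gives suitable standard errors whichever way the random-intercept error would run.

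The cost is a sentence in Section 11.0 and a line of code. The model has six covariance parameters instead of two for about 50 people per role, with a small loss of degrees of freedom. This is a cheap improvement, not a condition for the trial to proceed.
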